4.6 Core Lab Evaluations

Anonymised DICOM CT data will be transferred to the core lab from site electronically or via CD. CT data from baseline (the first CT scan after the index uTBAD) at six weeks after discharge from hospital (after conservative management or after TEVAR) and at one year and five years after randomisation.

Data will be analysed according to a specific core lab protocol.

Incidental findings will potentially be identified on review of CT scans in the core lab. In each case the incidental finding will be reported to the principal investigator of the site and local protocol will determine the treatment of the individual.

5. INTERVENTION

5.1 Thoracic endovascular aortic repair

The health technology being assessed is TEVAR, specifically used in participants in the subacute phase (defined as 10 days to 3 months) after uTBAD.

The aim of the stenting procedure will be to close the primary entry tear of the dissection, preventing flow into the false lumen and inducing positive remodelling of the aorta. This procedure has been shown to reduce the long-term risk of aortic dilatation (which if untreated leads to rupture) and requirement for aortic repair (see below).

Participants will undergo stenting of the aorta to close the primary entry tear with any CE marked thoracic stent device system.

All procedures should be planned on a 3D workstation as standard.

All participants must undergo anaesthetic assessment.

The procedure may be performed under general, local, or regional anaesthetic. Access to the arterial system will be via the common femoral artery either using a percutaneous approach (closed with any of the available closure devices) or after surgical cut down (with formal artery closure at the end).

Any reasonable adjunct/approach to provide safe access is permissible, including but not limited to adjunctive procedures such as fashioning of a conduit onto the iliac vessels to permit safe introduction of the delivery device.

When considering the landing zone of the stent the clinician must plan to: close the proximal entry tear; land the stent in healthy, non-dissected aorta; and aim for 2cm of landing zone measured from the proximal extent of the primary entry tear, however, in cases of dissection this is not a mandatory requirement if the operator is confident that a seal of the false lumen can be achieved.

In order to obtain a sufficient landing zone, the subclavian artery may be covered, with or without revascularisation with a carotid-subclavian bypass graft or standard endovascular technique to allow continued perfusion (e.g., chimney, fenestration/scallop, branch).

Single and staged procedures (as long as the aortic stenting is planned to take place between 10 days and 3 months after the presenting TBAD) will be permitted.

Confidential Page 27 of 30

EARNEST	Protocol No: 174766	Sponsor: London	Imperial	College	V1.0 7 th Oct 2024

A maximum oversizing of approximately 10% will be recommended, with estimation of the aortic size made at the level of the left subclavian artery. For some graft types a lower oversizing is advisable. The length of the stent used will be determined by the clinical team. We recommend coverage of 20-25cm of the thoracic aorta landing in a non-angulated segment as standard. However, the extent of aortic coverage will depend on many factors (including previous aortic repair, length of dissected area, secondary tears) that may influence the rate of paraplegia, and will be at the discretion of the operator ultimately.

Ancillary treatments to close the distal re-entry tears and reduce false lumen perfusion (such as the STABILISE technique) will not be recommended as part of the clinical guidelines, but centres will be able to utilise these techniques if deemed necessary by the operator or there are significant perceived advantages to the technique.

At the end of the procedure post-stent intra-arterial digital subtraction quality control images should be obtained.

Post-operative participants receiving TEVAR must be managed in a high dependency unit setting utilising established centre specific neurological protection strategies.

The procedure will take place in an operating theatre environment with mobile or fixed X-Ray imaging capabilities as per local standard operating procedures.

Stent graft follow-up will take place at local NHS institutions.

The procedural aspects and intervention adherence must be recorded using the TEVAR case report form.

5.2 Best medical therapy

All participants in both arms will receive BMT, which is standard of care in the UK, in an attempt to reduce the progression of aortic dilatation subsequent hospital admission rates, and the need for late dissection related aortic procedures.

Participants should receive treatment in accordance with the standard of care protocols established at each participating site. The BMT expectations will be informed by established guidelines including the European Society of Vascular Surgery guidelines, which are established practice in the UK, the 2010 American College of Cardiology and the American Heart Association "Guidelines for the Diagnosis and Management of Patients with Thoracic Aortic Disease".

Treatment goals will be to reduce aortic wall stress by controlling heart rate to less than 60 beats per minute and systolic BP less than 120mmHg. Specific treatment regimens will be on a patient specific basis at the discretion of local specialist teams.

We advise that all participants should undergo 24-hour BP recording within 6-weeks of admission for uTBAD. For those with a significant atherosclerotic risk the advice will be that BMT should be maximised by the addition of a statin and antiplatelet agent. Smoking cessation will be advised

Where clinically indicated according to local protocol, participants in both trial arms will receive intervention on the aorta (either secondary interventions in the TEVAR+BMT+SURV group or primary interventions (e.g. for aneurysmal degeneration) in

Confidential Page 28 of 30

EARNEST	Protocol No: 174766	Sponsor: London	Imperial	College	V1.0 7 th Oct 2024

the BMT+SURV group) which is standard of care in the UK according on current European Society of Vascular Surgery guidelines. In this pragmatic trial, we advise reference to the guidance provided by the European Society of Vascular Surgery [5], but the decision to treat will be at the discretion of the local clinical team.

5.3 Permanent Discontinuation of Study Intervention and Withdrawal from Study

(i) Permanent discontinuation of study intervention

Participants may not undergo the study intervention (TEVAR) for the following reasons:

- At the request of the participant.
- If the investigator considers that a participant's health will be compromised by the study intervention (TEVAR) due to Adverse Event/Serious Adverse Event or concomitant illness that develops after entering the study.

(ii) Withdrawal from Study

Withdrawal from the study refers to discontinuation of study procedures and can occur for the following reasons:

- Participant decision
- Loss to follow-up

(iii) Procedures for Withdrawal from Study

If a subject withdraws prematurely the reason for withdrawal will be recorded in the CRF/eCRF and medical records. All study visits up to the point of any planned withdrawal will be completed.

6. SAFETY REPORTING

6.1 Adverse Event (AE)

An AE is any untoward medical occurrence in a patient or clinical trial participant. An AE can therefore be any unfavourable and unintended sign (including an abnormal laboratory finding), symptom, whether or not considered related to the trial protocol.

6.2 Adverse Event recording

Adverse events will be recorded at each study visit. The following will be recorded for all adverse events:

- date of onset
- description of event
- frequency
- severity

Confidential Page 29 of 30

EARNEST	Protocol No:	Spansari	Imperial	Collogo	V1.0 7 th Oct 2024
EARNEST	174766	Sponsor: London	imperiai	College	V1.0 7 OCI 2024

- causality
- outcomes
- action taken.

For the purposes of the study, AEs will be followed up according to local practice until the event has stabilised or resolved, or the follow-up visit, whichever is the sooner. SAEs will be recorded throughout the study.

In this study, there may be a number of potential common aortic related events that occur which require hospitalisation but will not be required to be reported as SAEs but must be collected as AEs within the eCRF if the adverse event either occurs within 90 days of the index TEVAR procedure or is aortic related.

The following will be noted as a rtic related events:

- Any adverse event within 30 days of aortic surgery
- Access vessel dissection or rupture or pseudo-aneurysm
- Endoleak
- · Proximal or distal re-entry tears
- Graft kinking (requiring re-intervention or symptomatic)
- Graft migration of >5mm
- Graft thrombosis/stenosis/occlusion
- New onset limb ischaemia including new onset claudication
- Mesenteric ischaemia/angina
- New onset renal failure/deterioration
- Paralysis/paraparesis
- Stroke
- Amputation
- · Retrograde aortic dissection
- Aortic rupture/bleeding/
- Graft infection
- Re-intervention or any endovascular or open arterial procedure.

(iv)Severity of Adverse Events

The assessment of severity will conform to the following definitions:

Mild: Awareness of event but easily tolerated

Moderate: Discomfort enough to cause some interference with usual activity

Severe: Inability to carry out usual activity

Confidential Page 30 of 30

EARNEST	Protocol No: 174766	Sponsor: London	Imperial	College	V1.0 7 th Oct 2024

(v) Causality of Adverse Events

The assessment of causality will conform to the following definitions:

- Unrelated: No evidence of any causal relationship with the intervention or trial conduct
- Unlikely: There is little evidence to suggest there is a causal relationship with the intervention or trial conduct and there is another reasonable explanation for the event (e.g. the participant's clinical condition, other concomitant treatment).
- Possible: There is some evidence to suggest a causal relationship with the intervention or trial conduct. However, the influence of other factors may have contributed to the event (e.g. the participant's clinical condition, other concomitant treatments).
- Probable: There is evidence to suggest a causal relationship with the intervention or trial conduct and the influence of other factors is unlikely.
- Definite: There is clear evidence to suggest a causal relationship with the intervention or trial conduct and other possible contributing factors can be ruled out.

6.3 Serious Adverse Events (SAE) (vi)Definition of SAE

An SAE is defined as any event that

- Results in death;
- Is life-threatening*;
- Requires hospitalisation or prolongation of existing inpatient's hospitalisation**;
- · Results in persistent or significant disability or incapacity;
- Is a congenital abnormality or birth defect;
- * "Life-threatening" in the definition of "serious" refers to an event in which the participant was at risk of death at the time of the event; it does not refer to an event which hypothetically might have caused death if it were more severe.
- ** "Hospitalisation" means any unexpected admission to a hospital department. It does not usually apply to scheduled admissions that were planned before study inclusion or visits to casualty (without admission).

Medical judgement should be exercised in deciding whether an adverse event/reaction is serious in other situations. Important adverse events/reactions that are not immediately life-threatening, or do not result in death or hospitalisation but may jeopardise a participant or may require intervention to prevent one of the other outcomes listed in the definition above should also be considered serious.

Confidential Page 31 of 30

EARNEST	Protocol No:	Sponsor:	Imperial	College	V1.0 7 th Oct 2024
	174766	London			

6.4 Reporting of SAEs

Active monitoring of all participants after the end of the trial is required clinically but not as part of this study. If the investigator becomes aware of safety information that appears to be related to the trial, involving a participant who participated in the study, even after an individual participant has completed the study, this should be reported to the Sponsor.

All SAEs will be reviewed by the Chief Investigator or a designated medically qualified representative to confirm expectedness and causality. Reporting of SAEs and review by the CI will be via the trial data collection system (CRF/eCRF).

Reporting of all SAEs to the Sponsor is not required, unless they are related and unexpected.

(vii) Related SAEs

Related: resulted from administration of any of the research procedures. Expected SAEs are detailed in the study-specific Safety reporting instructions.

(viii) Unexpected SAEs

Unexpected: type of event is not listed in the protocol as an expected occurrence

(ix) Reporting of SAEs that are related and unexpected.

SAEs that are *related and unexpected* should be notified to the relevant REC and the Sponsor in accordance with local requirements.

Follow up of participants who have experienced a related and unexpected SAE should continue until recovery is complete or the condition has stabilised.

6.5 Reporting urgent safety measures

If any urgent safety measures are taken the CI/Sponsor shall immediately and in any event no later than 3 days from the date the measures are taken, give written notice to the relevant REC of the measures taken and the circumstances giving rise to those measures.

7. STATISTICAL ANALYSES

7.1 Sample Size and power considerations

The samples size has been calculated to be 470 participants (235 in each arm), followed up for 5 years.

Our power calculations were made after reviewing published data and re-analysis of data from the ETTAA national cohort study of patients with thoracic aortic aneurysms.[19] Primary outcome is the composite of aortic-related mortality AND/OR severe permanent neurological deficit AND/OR severe permanent cardiorespiratory failure.

Primary endpoint incidence in the SURV+BMT arm of the study: the estimated aortic-related mortality at 5 years is 14.8% taken from the combined results of one long term RCT, one high quality cohort study, and one propensity matched analysis [10, 20, 21]

Confidential Page 32 of 30

EARNEST	Protocol No: 174766	Sponsor: London	Imperial	College	V1.0 7 th Oct 2024

Because the control group has no intervention, the estimated early (up to 30 days) severe permanent neurological deficit and/or cardiorespiratory failure is assumed to be 0% for the BMT group. These complications were not observed in either of two RCTs or a propensity matched analysis in TEVAR or BMT groups.[9, 20, 21]

Using estimates from the INSTEAD trial, [21] the 5-year risk of surgery/stenting was 26.5% in the BMT group. 78% of these patients would be suitable for a stent, with the other 22% of patients requiring surgery. These later interventions are more likely to be complicated and/or emergency procedures, with late severe permanent neurological deficit/cardiorespiratory failure estimated at 8% for those undergoing stenting and 11.29% for open procedures (based on data from ETTAA and observational data from surgical series.[7, 19] Combining risk of a late intervention, with risk of severe permanent neurological deficit/cardiorespiratory failure after an intervention, we expect non-fatal components of the primary outcome (i.e., patients who do not die within five years) of 2.31%.¹

Adding the 14.8% of patients who die within 5 years, the early 30-day non-fatal event rate of 0%, and the longer term non-fatal serious event of 2.31%, *the estimated 5-year incidence* of the composite primary endpoint is 17.11% in the BMT group.

Primary endpoint incidence in the TEVAR+BMT arm: The estimated aortic-related mortality at 5 years is 5.39% taken from the combined results of one long term RCT and one high quality cohort study and one propensity matched analysis [10, 20, 21] This difference in mortality between SURV+BMT and TEVAR+BMT groups would be consistent with a HR of 2.71 estimated in a meta-analysis.[13]

The estimated sub-acute phase severe permanent neurological deficit is 1.02% for TEVAR+BMT group. Severe permanent cardiorespiratory failure was not observed in either of two RCTs or a propensity matched analysis in TEVAR+BMT or SURV+BMT groups.[9, 20, 21]

From the INSTEAD trial,[21] the risk of late intervention was 16.7% for the TEVAR+BMT group. 75% of these patients that would be suitable for a stent, with the other 25% of patients requiring open surgery. Our expert panel estimated a risk of severe permanent neurological deficit/cardiorespiratory failure of 2% (stenting) and 4% (open) of patients. This was based on a substantial decrease in the need for complex procedures in patients with previous intervention and a substantially decreased risk of emergency intervention, compared to control patients.[21] Combining risk of a late intervention, with risk of severe permanent neurological deficit/cardiorespiratory failure after an intervention, we expect non-fatal components of the primary outcome of 0.42%.²

Adding the 5.39% of patients who die within 5-years to the 1.02% who survive a sub-acute phase event and 0.42% who survive without a sub-acute phase event but have a serious event longer term, the estimated 5-year incidence of the composite primary endpoint is 6.83% in the TEVAR+BMT group.

Thus, if there is no crossover or loss to follow up, primary outcomes are expected in 17.11 patients in the SURV+BMT arm and 6.83 in the TEVAR+BMT arm.

Confidential Page 33 of 30

 $^{^{1}}$ 26.5% x 0.78 x 0.08 + 26.5% x 0.22 x 0.1129 = 2.31%

 $^{^{2}}$ 16.7% x 0.75 x 0.02 + 16.7% x 0.25 x 0.04 = 0.42%

EARNEST	Protocol No:	Sponsor:	Imperial	College	V1.0 7 th Oct 2024
	174766	London			

Overall: Assuming 2.5% cross-over from each arm (low estimated because TEVAR in the sub-acute phase can only occur between 10 days and 3-months), we would expect event rates of 16.85% (=17.11x0.975 + 6.83x0.025) in the TEVAR+BMT arm and 7.09% (=6.83x0.975 + 17.11x0.025) in the SURV+BMT arm. This corresponds to an average observed event rate over the two arms of 11.97% and a hazard ratio of approximately 0.4 for TEVAR+BMT, relative to SURV+BMT (estimated from hazards based on exponential time to event rates).

Using Stata v17.0 and command, (power cox, hratio(0.4) failprob(0.1197) effect(hratio) power(0.9)), for 90% power, and two-sided type-1 error 5%, we would require 51 events in 419 patients. Inflating this to allow 10% of patients to be lost to follow up (and censored at last visit in the primary analysis), we require 57 events in 470 patients (235 in each arm), followed up for 5 years (based on Cox regression for primary analysis). The estimand for our primary analysis is the hazard ratio for the comparison between TEVAR+BMT and SURV+BMT (see the separate Statistical Analysis Plan for full details of the methods for estimating the sample size).

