7.2 Planned recruitment rate

We estimate a single centre to open for the first 4 months, then recruit one centre a month until there are 25 (over 28 months). When open, the average recruitment per centre per month will be 0.7 participants.

At 18 months we expect 15 centres open, and 86 participants randomised. At the end of the internal pilot phase (at 18-months), the number of sites open to recruitment, recruitment rates and adherence to allocated treatments will be assessed

Red, amber and green outcomes will be set for recruitment, site opening and data completion. The outcome will be judged as RED if centres have recruited less than 30 participants which equates to less than 35% of the projected numbers at this stage; AMBER if centres have recruited 30-85 participants which equate to 35- 100% of the projected numbers at this stage; and GREEN if centres have recruited over 86 participants which equate to >100% of the projected numbers at this stage. At the end of the internal pilot the number of centres actively recruiting; data completion and visit completion at 6-weeks will be assessed in the same way.

Progression Criteria	Red	Amber	Green
Number recruited	<30 participants	30-86 participants	>86 participants
Number of sites opened	<5	5-15	>15
Data completion	<70%	70-85%	>85%
6-week clinical follow up completed	<70%	70-85%	>85%

Table 1: Progression criteria after 18 months of recruitment to the EARNEST trial generated using the internal pilot.

Predicted recruitment is 470 participants in the UK over 42-months, an average of 135 patients/year (we estimate this will be 1 in 4 patients with acute uTBAD presenting to sites).

Confidential Page 34 of 30

EARNEST	Protocol No:	Spansari	Imperial	Collogo	V1.0 7 th Oct 2024
EARNEST	174766	Sponsor: London	imperiai	College	V1.0 7 OCI 2024

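### Section 7 misstates three planning figures: the post-cross-over event rates are on the wrong arms, the event requirement is 51 and not 57, and the text leaves 86 recruits in no pilot band

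*Protocol*

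**What the plan says.** Protocol Section 7.1 builds up 5-year incidences of the primary composite before cross-over: 17.11% for SURV+BMT and 6.83% for TEVAR+BMT. It then allows 2.5% cross-over from each arm and writes "we would expect event rates of 16.85% (=17.11x0.975 + 6.83x0.025) in the TEVAR+BMT arm", giving 7.09% to SURV+BMT. From these it derives a mean rate of 11.97% and "a hazard ratio of approximately 0.4 for TEVAR+BMT, relative to SURV+BMT".

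The sample size follows from Stata's power cox command: "for 90% power, and two-sided type-1 error 5%, we would require 51 events in 419 patients". After an allowance of 10% for loss to follow-up, with those lost censored at their last visit, the conclusion is "we require 57 events in 470 patients (235 in each arm), followed up for 5 years".

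Section 7.2 gives the pilot projection: "At 18 months we expect 15 centres open, and 86 participants randomised". The text then has "AMBER if centres have recruited 30-85 participants which equate to 35- 100% of the projected numbers at this stage", with GREEN above 86, described as more than 100% of projection. Table 1 in the same section gives AMBER as "30-86 participants" and GREEN as more than 86. For sites, Table 1 has AMBER at 5 to 15 and GREEN above 15.

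**The concern.** These are three separate errors in figures that other people will use.

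- **Arm labels.** The weights in the formula contradict the labels. Read literally, the protocol expects more events with TEVAR, against the paragraphs before it and the hazard ratio after it.
- **Required events.** The number of events that gives a stated power depends on the hazard ratio, the error rates and the allocation. It does not depend on how many patients drop out. Carrying the dropout inflation over to the events produces a requirement that the power statement does not support, and anyone tracking accrued events would be comparing them with the wrong figure.
- **Pilot bands.** Text and table disagree at exactly the projected number, which is the value where a clear rule is most needed.

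**Working it through.** **Inputs, all from the Protocol.** Section 7.1: 17.11% and 6.83% before cross-over; 2.5% cross-over from each arm; hazard ratio 0.4; mean event probability 0.1197; two-sided 5%; 90% power; 10% loss. Section 4.3: 1:1 allocation. Section 7.2: one centre for the first 4 months, then one more each month up to 25; 0.7 participants per centre per month.

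**1. Arm labels**

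- SURV+BMT: 17.11 × 0.975 + 6.83 × 0.025 = 16.853, i.e. 16.85%.
- TEVAR+BMT: 6.83 × 0.975 + 17.11 × 0.025 = 7.087, i.e. 7.09%.
- Mean: (16.853 + 7.087)/2 = 11.97%, as stated.
- Hazard ratio for TEVAR+BMT from exponential hazards: ln(1 − 0.07087)/ln(1 − 0.16853) = 0.398, which is the stated 0.4.
- With the printed labels the ratio inverts: 1/0.398 = 2.51.

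The arithmetic is right; only the arm names are exchanged.

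**2. Required events**

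The plan's own figures come first, using the Schoenfeld formula:

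- Events = (1.960 + 1.282)² / (0.25 × (ln 0.4)²) = 10.507/(0.25 × 0.8396) = 50.06, rounded up to 51.
- Patients = 50.06/0.1197 = 418.2, rounded up to 419.

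Both match the protocol. Next, the loss allowance:

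- Patients: 419/0.9 = 465.6, so 466. The stated 470 is slightly above this.
- Events: the protocol does not show how 57 arises. It equals 51/0.9 = 56.7 rounded up, and also 470 × 0.1197 = 56.3 rounded up. The first inflates events for dropout, which is not valid. The second is what 470 patients would yield with no loss at all. Neither is a requirement for 90% power.
- Power at hazard ratio 0.4, from Φ(0.5 × √d × |ln 0.4| − 1.96): d = 51 gives 90.5%; d = 57 gives 93.3%.

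The expected yield is a different quantity and depends on follow-up.

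| Follow-up | No loss | 10% lost, contributing half their risk | 10% lost, contributing no events |
|---|---|---|---|
| Everyone stops at 5 years | 56.3 | 53.4 | 50.6 |
| Everyone followed until the last participant reaches 5 years | about 69 | about 65 | about 62 |

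The first row is 470, 446.5 or 423 patients × 0.1197. The second row uses the Section 7.2 accrual model over 42 months, which gives mean follow-up of about 6.2 years, with constant hazards; the event probability becomes about 0.146. The two loss patterns are assumptions that bracket the range.

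**3. Pilot bands**

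- Centre-months by month 18: 4 × 1 + (2 + 3 + … + 15) = 4 + 119 = 123. Recruits: 123 × 0.7 = 86.1, with 15 centres open. The projection reproduces.
- Text, by count: 85 is AMBER, 87 is GREEN, and 86 is neither.
- Text, by percentage: AMBER runs to 100%. 86/86 is 100%, so 86 is AMBER; 85/86 is only 98.8%, so the count of 85 does not match the percentage beside it.
- Table 1: 86 is AMBER.

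The text's percentages and Table 1 agree. The count of 85 in the text is the one that does not fit.

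**The case against.** The strongest reply is that none of this affects the design. The correct rates stand in the paragraphs just before the swap, the hazard ratio just after it has the right direction, and 11.97%, 51, 419 and 470 do not depend on the labels. That is right, and the swap should be described as a labelling slip.

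A reader might infer from the 57 that the trial fails its own requirement by design, because only about 51 to 54 events are expected. The document does not support that. Section 7.3 ties the primary analysis to all participants being at least 5 years past randomisation; there is no event trigger and no interim efficacy analysis. The shortfall also needs follow-up to stop at exactly 5 years. Section 7.1 and the visit schedule suggest this, but the Trial Summary and Sections 1.7 and 2.1 speak of a minimum of 5 years, and Section 1.9 censors at the end of the study. On that reading the expected yield is about 62 to 65 events with 10% loss, above 57.

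A reader might also infer that it is an error for a pilot exactly on plan to be AMBER, for recruits and for sites. It is strict, but it is the stated rule: the text reserves GREEN for more than 100% of projection, and Table 1 applies that to both criteria. Lowering GREEN to include 86 recruits or 15 sites would be a design preference. The site band contains no contradiction.

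What stands after this is the wrong labels, the wrong requirement and the text-table mismatch at 86.

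**Conclusion.** The point holds for three specific statements.

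- The rates after cross-over are 16.85% for SURV+BMT and 7.09% for TEVAR+BMT. This follows from the protocol's own formulas and needs no assumption.
- The event requirement for 90% power is 51, given hazard ratio 0.4, two-sided 5% and 1:1 allocation. The stated 57 is 6 too many and corresponds to about 93% power.
- The text and Table 1 disagree on whether 86 recruits is AMBER, and by count the text assigns 86 to no band.

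The sample size of 470, the hazard ratio of 0.4 and power near 90% are unaffected. With 10% lost and follow-up stopped at 5 years, the expected 51 to 54 events lie at or close to the requirement of 51. The errors are definite but limited. They are worth correcting because they sit in the sample-size justification and in the progression criteria.

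**What to change.** 1. In Section 7.1, exchange the two arm names so that 16.85% is SURV+BMT and 7.09% is TEVAR+BMT.
2. In Section 7.1, replace the statement that 57 events are needed with: 51 events are required; 470 patients are randomised to allow for 10% loss to follow-up. If an expected yield is also given, state the follow-up it assumes: about 51 to 54 events with 10% loss if follow-up stops at 5 years, and more if it continues to the end of the study.
3. In Section 7.2, make text and table agree. The smallest change is to raise the upper limit of AMBER in the text from 85 to 86, which matches both Table 1 and the percentages in the text. The site band can stay as it is.

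The cost is two labels, one sentence and one number. Sample size, analysis and progression rule do not change.
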